 12. History of intolerance to 5-MeO-DMT, dimethyltryptamine (DMT), or related compounds
 13. Any nasal obstruction, blockage, or symptoms of congestion
 14. Any personal or family history of malignant hyperthermia
 15. Disposition judged by the Investigator (or delegate) to be incompatible with establishment of rapport with study team and/or safe exposure to BPL-003
 16. Presence of acute or chronic illness or infection or history of chronic illness or infection sufficient to invalidate the patient's participation in the study or make it unnecessarily hazardous
 17. Presence or history of severe adverse reaction to any drug or drug excipient
 18. Female patients who are pregnant or lactating or of childbearing potential and not willing to use adequate forms of contraception during the study and for 1 month after completion of the study, as described in Section 6.2.4
 19. Male patients who are sexually active and not willing to use adequate forms of contraception during the study and for 1 month after completion of the study, as described in Section 6.2.4

20. Patients who have taken part in a clinical research study in the last 4 weeks, whether or not they received an investigational medicinal product as part of that research study
21. Current criminal justice involvement with legal proceedings, which in the opinion of the Investigator means the participant may fail to complete the study protocol due to re-incarceration or relocation from the clinic's catchment area
22. Unable to communicate in English to a level required to accept standard care and psychosocial intervention
23. Patients who, in the opinion of the Investigator, are not suitable to participate in the study for any other reason not mentioned in the entry criteria

5.2.2.2. Psychiatric Exclusion Criteria:

1. Personal or first-degree family history of schizophrenia, bipolar disorder, psychotic disorder (unless substance induced or due to a medical condition), delusional disorder, paranoid disorder, or schizoaffective disorder, as defined by DSM-5. Personal history determined by medical records and positive diagnoses on the Mini-International Neuropsychiatric Interview (MINI version 7.02) to be confirmed by the Investigator
2. Any major psychiatric disorders, with the exception of mild or moderate anxiety and/or depression, as determined by a MINI and confirmed by the Investigator
3. A clinical diagnosis of post-traumatic stress disorder (as determined by MINI)
4. Psychological therapies other than those planned per protocol that are initiated or terminated within 21 days of baseline and for the duration of the study
5. Has suicidal ideation with some intent to act within the 12 months before Screening, per the Investigator's clinical judgment or based on the Columbia-Suicide Rating Scale (C-SSRS), corresponding to a response of "Yes" on Item 4 (active suicidal ideation with some intent to act, without specific plan) or Item 5 (active suicidal ideation with specific plan and intent) for suicidal ideation on the C-SSRS, or a history of suicidal behaviour within the 12 months before Screening. Suicidal ideation with intent to act or suicidal behaviour as assessed on Day -3 should also be excluded
6. Suicide attempts and/or self-injurious behavior within 12 months before Screening.
7. Regular use of or dependence on other drugs other than caffeine or nicotine. Presence or history of SUD (not including AUD) as defined by the DSM-5. The Investigator will evaluate the patient's ability to abstain from using this substance during the study. The patient must have a negative recreational drug test on Day 0, before dosing
8. Any self-reported use of psychedelic compounds (phenethylamines, tryptamines, or dissociatives) in the past 6 months

5.3. Patient Withdrawal Criteria

Patients are free to withdraw from the study at any time without giving reasons. Furthermore, the Investigator may withdraw a patient for reasons such as intolerance to study drug, intercurrent illness, need for medication which is contraindicated, significant noncompliance with the

requirements of the study, or withdrawal of consent. The Investigator will assess the reasons for withdrawal as far as possible and will fully record the circumstances and medical details.

Patients will be informed before they agree to take part in the study that if they withdraw or are withdrawn:

- The Investigator will stop collecting information about them; and
- They can ask the Investigator to destroy any identifiable samples taken from them.

The Investigator will ask withdrawn patients to have a follow-up examination, to check that they have come to no harm as a result of taking part in the study. Provided that the patient agrees, they will undergo, at withdrawal from the study (or as soon as possible afterwards), all assessments scheduled for the final Follow-up Visit. If patients withdraw after dosing but before completing the scheduled assessments, they will also be required to complete a psychological assessment before discharge from the clinic. The Investigator will record in the case report form (CRF) the results of the follow-up examination of withdrawn patients.

Withdrawn patients will be replaced at the discretion of the Sponsor and Investigator.

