5.2. Patient Inclusion and Exclusion Criteria

5.2.1. Diagnosis and Main Criteria for Inclusion

To be eligible to participate in this study, patients must meet the following criteria:

1. Willing and able to give informed consent
2. Age 18 to 64 years at Screening
3. Diagnosed with moderate to severe AUD (based on DSM-5)
4. Minimum of 4 HDD in the 28 days before Screening
5. No more than 14 days after the last HDD or completion of detoxification (at point of screening), with no HDD in the 72 hours prior to dosing, and no alcohol at all in the 24 hours prior to dosing
6. Willing to abstain from using recreational drugs from Screening until end of the study
7. Willing to abstain from smoking during their time in the clinic on the day of drug administration as instructed by clinical staff
8. Willing to refrain from psychedelic drug use (excluding the study drug) from Screening until the end of the study
9. Able (in the Investigator's opinion) and willing to undertake and comply with all study requirement, with the ability to complete all protocol-required assessment tools and to comply with all study visits
10. Willing to allow their own general practitioner, and consultant if appropriate, to be informed of study participation
11. Living in stable/secure accommodation in the community
12. In possession of a personal mobile phone and able to nominate at least one locator individual (e.g., a family member, friend, or recovery mentor) with a verifiable address and a telephone number to assist with the arrangement of follow-up appointments

5.2.2. Exclusion Criteria:

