6. TREATMENT OF PATIENTS

6.1. Description of Study Drug

Patients will receive a single intranasal dose of BPL-003. The dose selected will be based on the PK, PD, safety, and tolerability data from the completed study BPL-003-103.

Doses will be delivered using the Aptar Unidose (UDS) intranasal dry powder delivery system. Each dose is preloaded into the delivery device. Further details may be found in [Section 7.1](#).

All doses will be administered by a trained member of the study team, in the presence of a psychiatrist and therapist.

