6.2.2. Previous and Concomitant Treatment

Previous and current treatment restrictions are described in [Section 5.2.2](#).

During the study, concomitant medication may be given if the patient's personal physician believes it to be necessary. In addition, paracetamol (acetaminophen) will be allowed each day for mild analgesia. It should be given in line with package label/instructions. Administration of COVID-19 vaccination will also be allowed (see [Section 4.5.1](#)). Any other concomitant treatment will be given only if deemed strictly necessary by the Investigator. In any case, all concomitant treatments will be reported in the eCRF along with their daily dosage, duration, and reasons for administration. Patients who have received any concomitant treatment may be withdrawn from the study at the discretion of an Investigator.

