10.2.5. Follow-up of AEs and SAEs and Assessment of Outcome

After the initial AE/SAE report, the Investigator is required to proactively follow each patient and provide further information on the patient's condition.

All AEs and SAEs documented at a previous visit/contact and designated as not recovered/not resolved or recovering/resolving will be reviewed at subsequent visits/contacts.

Investigators will follow up patients

- With at least 1 SAE or patients withdrawn from the study due to an AE, until the event has resolved, subsided, or stabilised; the event is otherwise explained; or the patient is lost to follow-up
- In the case of other nonserious AEs, patients will be followed until they complete the study or are lost to follow-up
- The Investigator should not conclude that the patient is lost to follow-up earlier than 30 days after discontinuation of study drug

Clinically significant laboratory abnormalities will be followed up until they have returned to normal or a satisfactory explanation has been provided. Additional information (including but not limited to laboratory results) relative to the subsequent course of such an abnormality noted for any patient must be made available to the Investigator. If a clinically significant laboratory abnormality is reported as an AE, the Investigator will determine the severity and relatedness of the event.

The outcome of any nonserious AE or any SAE reported during the entire study will be assessed as follows:

- Recovered/resolved

- Not recovered/not resolved
- Recovering/resolving
- Recovered with sequelae/resolved with sequelae
- Fatal (SAEs only)

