12.1 Premature withdrawal and missing data

All patients who withdraw prematurely from the study or study drug will be included in the statistical analyses.

If a patient completes the treatment period but has missing data, then this will be made apparent in the patient listings. Missing data will not be imputed.

If the study is prematurely discontinued, all available data will be listed and a review will be carried out to assess which statistical analyses are still considered appropriate.

Data collected at unscheduled time points during the study will not be used in the summaries or data analyses. They will be included in the listings.

If time information (ie hours and/or minutes) for adverse events (AEs) or concomitant medication is missing, but the day is present, then the time will be calculated in days. If date information is partial or missing, then any derived times (eg AE start time from last study medication) will be listed as missing.

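### Section 5.3 ends data collection for patients withdrawn after the single dose, contradicts its own exit visit and Section 10.2.5, and risks favourable bias in later results

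*Protocol*

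**What the plan says.** Dosing happens once: "Patients will receive a single intranasal dose of BPL-003" (Protocol 6.1). Weekly relapse prevention sessions continue for 12 weeks after it, and visits run to Day 84 (6.6, Table 1).

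- **Who may be withdrawn.** Section 5.3 lets the Investigator withdraw a patient for reasons such as "intolerance to study drug, intercurrent illness, need for medication which is contraindicated", significant noncompliance, or withdrawn consent. Section 6.2.2 adds: "Patients who have received any concomitant treatment may be withdrawn from the study at the discretion of an Investigator". The same section permits paracetamol, COVID-19 vaccination and treatment judged necessary.
- **What follows.** Under 5.3 patients are told before agreeing to take part that, whether they leave or are taken out, "The Investigator will stop collecting information about them". The section then asks withdrawn patients to attend a follow-up examination. If they agree, they complete the last-visit assessment set, and the examination results go in the CRF.
- **Adverse events.** Section 10.2.5 requires follow-up of patients "With at least 1 SAE or patients withdrawn from the study due to an AE, until the event has resolved, subsided, or stabilised". It also states: "The Investigator should not conclude that the patient is lost to follow-up earlier than 30 days after discontinuation of study drug". Inclusion criterion 12 (5.2.1) requires a locator individual "with a verifiable address and a telephone number to assist with the arrangement of follow-up appointments".
- **Analysis.** Everyone dosed is in the Safety population, and those with a PD measure are in the ITT population (SAP 9). SAP 12.1 includes premature withdrawals in the analyses, but "Missing data will not be imputed", and unscheduled measurements are listed without being summarised. SAP 12.3 defines no assessment windows. SAP Appendix A 4.2 computes the percentage and mean-per-day drinking measures over periods from Day 0 to Days 14, 28, 56 and 84. It gives no rule for a partly observed period and no censoring rule for days to first drink or first heavy drinking day.

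**The concern.** In a study with repeated dosing, withdrawing a patient can protect that patient by stopping the drug. Here there is no further drug to stop. What withdrawal can end is the psychotherapy and the record of what happened after the dose.

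Section 5.3 treats a patient who refuses further data collection in the same way as one whom the Investigator takes out for another reason. The stated reasons (intolerance, illness, needing another medicine, not complying) are plausibly connected with doing badly. If collection stops for those patients, the data lost are not a random sample.

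Safety is the primary objective. The C-SSRS and the Reactivation Questionnaire (ReAQ) both feed primary endpoints, and both are sparse late in follow-up. After Day 7 the C-SSRS is scheduled only at Day 84, and the ReAQ only at Days 28 and 84. With at most 12 patients, each one is 1/12 = 8.3% of the cohort.

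**Working it through.** The plan gives no figure to reproduce. It states no hypothesis test, power calculation or dropout rate. The check therefore sets the rules side by side and then illustrates the possible size.

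**1. Rules against each other**

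| Situation after dosing | Section 5.3 | Other text |
|---|---|---|
| Any withdrawal | Collection stops | The same section asks for an exit assessment, with results in the CRF |
| Withdrawn because of an AE, or has an SAE | Collection stops | 10.2.5: follow until resolved, subsided, stabilised, explained or lost |
| Takes another medicine | May be withdrawn if it is contraindicated | 6.2.2: any concomitant treatment may lead to withdrawal, though several are permitted. 6.2.1 calls the Appendix 1 list prohibited during the study, but most entries there run only until after the last dose |

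A site cannot honour both the statement to patients and 10.2.5. What counts as contraindicated after Day 0 is also unclear.

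**2. What remains and what can go missing**

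Data up to withdrawal are kept. With agreement there is one exit assessment, and the Day 84 set includes TLFB, AEs, C-SSRS, ReAQ, laboratory tests, EtG and CDT. After that point later non-serious AEs, C-SSRS, ReAQ and TLFB have no stated route into the data. The SAP does not assign the exit assessment to a visit. If it is classed as unscheduled, it is listed and left out of the summaries.

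**3. Possible effect on drinking** (assumed values, not document figures)

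Let 12 be dosed and k withdrawn. Completers average c = 20% heavy drinking days over Day 0 to 84, and the withdrawn would have averaged w. The Day 84 summary uses completers only.

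Full-cohort mean = [(12 − k)·c + k·w]/12. Understatement = (k/12)·(w − c).

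| k | w = 40% | w = 60% | w = 80% |
|---|---|---|---|
| 1 | 21.7 (1.7 points) | 23.3 (3.3) | 25.0 (5.0) |
| 2 | 23.3 (3.3) | 26.7 (6.7) | 30.0 (10.0) |
| 3 | 25.0 (5.0) | 30.0 (10.0) | 35.0 (15.0) |

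The observed mean is 20% in every cell. For a binary outcome, suppose 6 of 12 do well and all k withdrawn do poorly. The observed rate moves from 6/12 = 50% to 6/11 = 54.5%, 6/10 = 60.0% or 6/9 = 66.7%.

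**4. Possible effect on late safety**

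For AE percentages taken over all 12 dosed, an unseen late event counts as no event. If 3 of 12 would have a late event (25.0%), missing one gives 2/12 = 16.7% and missing two gives 1/12 = 8.3%.

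The chance of seeing at least one late event is 1 − (1 − p)^n:

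| True rate p | n = 12 | n = 10 | n = 9 |
|---|---|---|---|
| 10% | 71.8% | 65.1% | 61.3% |
| 20% | 93.1% | 89.3% | 86.6% |

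**The case against.** The documents contain real safeguards. Withdrawn patients are not removed from the analysis populations. A reaction that prompts withdrawal has already been recorded and counts in the TEAE percentage. The exit assessment is the full Day 84 set, a patient leaving before completing scheduled assessments also has a psychological assessment before discharge, and serious or AE-related cases are followed up. The drinking periods are cumulative from Day 0, so exit TLFB data can complete earlier periods. Alcohol use is exploratory. All of this stands and limits the point to later data.

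Four stronger readings are tempting and are not supported:

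- A reader might infer that withdrawal stops only the data. The intervention under study includes weekly psychotherapy, which may also end.
- A reader might infer that the worst-doing patients vanish from the safety results. They remain, with data to withdrawal. Relapse is not a listed reason, and both withdrawal clauses are discretionary, so selective loss is a risk and not a planned outcome.
- A reader might take the 30-day lost-to-follow-up rule to leave Days 31 to 84 unprotected (54 of 84 days, 64%). It is a floor on declaring loss, not permission to stop. Section 10.2.4 records AEs to the end of the Follow-up Visit or 30 days after dosing, whichever is later. The 64% therefore measures no loss. What is true is that wording about discontinuing study drug does not fit a single dose.
- A reader might assume that the two sites will use their discretion differently. Nothing in the documents shows this.

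The safeguards do not close the gap. The exit assessment needs agreement, happens once, captures nothing afterwards and has no assigned place in the SAP.

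**Conclusion.** The point holds in limited form. Section 5.3 states a rule that contradicts its own exit visit and Section 10.2.5. Applied as written, it can remove later non-serious AEs, C-SSRS, ReAQ and TLFB data from patients whose reason for leaving is plausibly related to outcome. Because the SAP uses observed data only and does not place exit data or partial periods, the later summaries risk a favourable bias.

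For heavy drinking days the illustrated understatement is 1.7 to 15.0 percentage points. It rests on 1 to 3 withdrawals in 12, on the assumed means, and on the withdrawn contributing nothing to the Day 84 period. If nobody is withdrawn, or those withdrawn resemble completers, there is no bias. The contradiction between sections does not depend on these assumptions. The plan should be amended.

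**What to change.** 1. **Protocol 5.3 and consent form.** Limit the statement that collection stops to patients who withdraw consent to further data collection. For any other ending of participation after dosing, and with the patient's agreement, continue AEs, concomitant medication, C-SSRS, ReAQ and TLFB to Day 84. State expressly that these contacts may be remote, because Table 1 note 2 otherwise excludes Days 28, 56 and 84 from remote conduct.
2. **Protocol 5.3, 6.2.2, 10.2.5 and Appendix 1.** Reconcile what they say about withdrawal after dosing. This review does not propose when a patient may be withdrawn.
3. **Protocol 10.2.5.** Tie the lost-to-follow-up floor to the Day 84 visit window, which closes at 84 + 4 = Day 88, and to failed contact through the locator individual already required at entry.
4. **SAP 12.1, 12.3 and Appendix A 4.2.** Assign exit-visit and late-contact data to a visit or TLFB period so that they enter the summaries. State how partial TLFB periods are handled. Censor days to first drink and first heavy drinking day at the last TLFB contact. TLFB is retrospective, so one late contact can recover missed days.

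The cost is amended protocol and consent wording, a few extra contacts and minor SAP work. No new instruments or patients are needed.

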6. TREATMENT OF PATIENTS

6.1. Description of Study Drug

Patients will receive a single intranasal dose of BPL-003. The dose selected will be based on the PK, PD, safety, and tolerability data from the completed study BPL-003-103.

Doses will be delivered using the Aptar Unidose (UDS) intranasal dry powder delivery system. Each dose is preloaded into the delivery device. Further details may be found in [Section 7.1](#).

All doses will be administered by a trained member of the study team, in the presence of a psychiatrist and therapist.

6.2. Concomitant Medications

6.2.1. Prohibited Medications

A list of medications prohibited during the study is provided in [Appendix 1](#).

6.2.2. Previous and Concomitant Treatment

Previous and current treatment restrictions are described in [Section 5.2.2](#).

During the study, concomitant medication may be given if the patient's personal physician believes it to be necessary. In addition, paracetamol (acetaminophen) will be allowed each day for mild analgesia. It should be given in line with package label/instructions. Administration of COVID-19 vaccination will also be allowed (see [Section 4.5.1](#)). Any other concomitant treatment will be given only if deemed strictly necessary by the Investigator. In any case, all concomitant treatments will be reported in the eCRF along with their daily dosage, duration, and reasons for administration. Patients who have received any concomitant treatment may be withdrawn from the study at the discretion of an Investigator.

6.2.3. Rescue Medication

Benzodiazepines, including oromucosal midazolam, and other suitable tranquilising treatment will be available as rescue medication, if needed. Oromucosal midazolam 2.5 to 5 mg by mouth (PO) or lorazepam injection 0.5 to 2 mg intramuscular (IM) will be offered as a first-line treatment. Risperidone 2 to 4 mg PO or aripiprazole 9.75 mg IM will be offered as a second-line treatment. These treatments will be given under the supervision of a psychiatrist.

6.2.4. Contraception and Pregnancy

At screening, the Investigator (or designee) will confirm that the patient has selected/is using an appropriate method of contraception. The Investigator will also confirm that the patient has been instructed in the consistent and correct use of that contraception, and will document the conversation and the patient's affirmation in the patient's records. In addition, the Investigator or designee will instruct the patient to call the clinic immediately if the selected contraception method is discontinued, or if pregnancy is known or suspected in the patient (pregnancy reporting is described in [Section 10.2.6](#)).

Patients must use a reliable method of contraception during the study, as follows.

Men

During the study and for 1 month after the final follow-up visit, male patients must not have sex without using a condom if their partner is a woman of childbearing potential. They do not need to use any contraception if their partner is not of childbearing potential. Partners who are not of childbearing potential are defined as men; postmenopausal women (no menstrual periods for at least 12 months); or women who have no uterus, ovaries, or fallopian tubes.

Patients must not plan to father a child or donate sperm during the study and for 1 month after their final follow-up visit.

Women

All female patients who are of childbearing potential must agree to use a highly effective method of contraception during the study and for at least 30 days after their follow-up visit. They must have been using that method for at least 28 days before the start of the study.

Highly effective methods of contraception are those that result in a failure rate of less than 1% per year when used consistently and correctly and include the following:

1. Combined or progestogen-only hormonal contraception associated with inhibition of ovulation (oral, intravaginal, transdermal, injections or implants)
2. Intrauterine device (IUD)
3. Intrauterine hormone-releasing system (IUS)
4. Bilateral tubal occlusion
5. Vasectomised partner (with surgical success)

A woman is considered to be of non-child-bearing potential if she meets one of the following criteria:

- Is postmenopausal (no menses for least 12 months without alternative medical cause; FSH at screening confirms postmenopausal status)
- Has no uterus, ovaries, or fallopian tubes

Women who are taking hormone replacement therapy can continue to do so during the study, but they must use contraception (as described above).

Patients who practice true abstinence or who only have same-sex relationships need not use contraception, provided it is in line with their preferred and usual lifestyle. Note: periodic abstinence [e.g., calendar, ovulation, symptothermal, and post-ovulation methods] and withdrawal are not acceptable methods of contraception). Should any such patient stop practising true abstinence, they must use contraception as described above.

